A Randomized Controlled Trial of patients undergoing Percutaneous Coronary Intervention who receive Ticagrelor and Fentanyl

FACTPCI (Fentanyl and Crushed Ticagrelor PCI) trial

Protocol dated October 28, 2019

Principal Investigator: [name] MD

Sub-Investigators:

[name] MD, [name] MD, [name] MD and [name] MD.

The Guthrie Clinic
[name]
[name]

Background:

[figure not shown]
Ticagrelor is an orally administered P2Y12 receptor antagonist in patients undergoing percutaneous coronary intervention (PCI).¹ Ticagrelor inhibits platelet activation and aggregation. Fentanyl is routinely administered as conscious sedation during the PCI procedures. Recent studies have shown that Opioid analgesics delay P2Y12 receptor antagonist mediated platelet aggregation.² Delay in platelet aggregation could lead to increased adverse events including stent thrombosis, myocardial infarction and death. In a recent trial, impact of Fentanyl on Ticagrelor mediated platelet aggregation was evaluated.³ There was delayed platelet aggregation with increased adverse clinical events in patients receiving Fentanyl and Ticagrelor. This was felt to be related to decreased absorption of Ticagrelor leading to delayed platelet aggregation. However, a recent study showed that crushed Ticagrelor has more bioavailability and reaches peak earlier than oral Ticagrelor.^{4, 5} Based on these results, it could be hypothesized that crushed Ticagrelor might mitigate some of the ill effects of Fentanyl. Hence, we propose this trial to assess the impact of Fentanyl on platelet aggregation in patients receiving crushed Ticagrelor during PCI.

Objective:

The primary objective is to test the influence of Fentanyl on pharmacodynamics of crushed vs non-crushed ticagrelor in patients who are undergoing PCI.

Methods & design:

Single center, randomized clinical trial designed to assess the influence of Fentanyl on pharmacodynamics of crushed vs non- crushed ticagrelor in patients undergoing PCI at Robert Packer Hospital. The plan is to enroll 80 patients in this study. Forty patients each in the elective and non-elective PCI groups. Further In each group, patients will be randomized in a 1:1 ratio to either crushed or non-crushed Ticagrelor arms.

Inclusion criteria:

- Patients \geq 18 years of age
- Undergoing clinically indicated elective or non-elective PCI
- Able to swallow oral medications

Exclusion criteria:

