The potential benefit to patients is that crushed Ticagrelor may have more bioavailability and reach peak earlier than non-crushed Ticagrelor. Crushed Ticagrelor may be useful to use following conscious sedation with Fentanyl, and may counter the delay in P2Y12 receptor antagonist mediated platelet aggregation that is associated with Fentanyl. Improved inhibition of platelet aggregation may lead to reduced adverse events including stent thrombosis, myocardial infarction and death.

For patients who are randomized to receive the non-crushed Ticagrelor, there is no anticipated benefit as this would be what is routinely done.

Study endpoints:

- The primary endpoint is the area under the PFT-time curve (AUC (0–6)) for the first 6 hours after the loading dose of Ticagrelor
- The secondary end points at discharge and 30 days are as follows -
 - Stent thrombosis
 - Recurrent myocardial infarction
 - All-cause mortality
 - Stroke
 - TIMI minor and major

Data Collection:

Information regarding patient characteristics will be obtained from the electronic medical record. Data will include: medical record number; age; sex; race; BMI; and medical history; date of PCI; radial or femoral access of the procedure; type of implanted stent; crushed or non-crushed ticagrelor; platelet function testing at baseline, 30 min, 2, 4, and 6, hours. Data will be collected at discharge and 30 days to include events of: stent thrombosis, recurrent myocardial infarction, all-cause mortality, stroke, or TIMI.

Statistics

- All continuous data will be expressed as mean \pm standard deviation and compared

- using a two-tailed Student's t-test when appropriate or the Mann-Whitney U test.
- Categorical variables will be expressed as a percentage and compared using chi-square or Fisher's exact test when appropriate.

Discussion:

This study is expected to provide crucial data on the influence of Fentanyl on crushed vs non-crushed Ticagrelor associated platelet function in patients undergoing PCI. The findings of this study would have a major impact on clinical practice as Fentanyl is currently used as sedation in more than 95% of patients undergoing PCI.

References:

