The primary objective is to test the influence of Fentanyl on pharmacodynamics of crushed vs non-crushed (integral) ticagrelor in patients who are undergoing PCI.

Study Design

a. Study Overview

Research location

The study is conducted at The Guthrie Clinic, Robert Packer Hospital, [name].

Design and Hypotheses

The study is a single center, randomized clinical trial designed to assess the influence of Fentanyl on pharmacodynamics of crushed vs non- crushed ticagrelor in patients undergoing PCI at Robert Packer Hospital.

Hypothesis: In patients undergoing PCI who receive fentanyl for conscious sedation, *crushed* ticagrelor produces faster and greater inhibition of platelet function over the first 6 hours after a loading dose than *non-crushed* ticagrelor, as measured by a smaller AUC_{0-6} of the platelet-function test.

- **H_0 (null):** There is no difference in the AUC_{0-6} of platelet function between fentanyl-sedated PCI patients receiving crushed ticagrelor and those receiving non-crushed ticagrelor.
- **H_1 (alternative):** The AUC_{0-6} of platelet function is lower (indicating greater platelet inhibition) in fentanyl-sedated PCI patients receiving crushed ticagrelor compared with non-crushed ticagrelor.

Summary of Endpoints:

- The primary endpoint is the area under the Platelet Function Testing (PFT)-time curve (AUC_{0-6}) for the first 6 hours after the loading dose of Ticagrelor.
- The secondary end points at discharge and 30 days:
 - Stent thrombosis
 - Recurrent myocardial infarction
 - All-cause mortality
 - Stroke
 - TIMI minor and major

b. Study Groups

Recruitment and Consent

Recruitment: Participants will be recruited from Robert Packer Hospital patients who are undergoing elective or non-elective PCI. Participants will be screened for eligibility and those who meet the inclusion/exclusion criteria will be invited to take part.

Consent: Written consent will be required for all study participants prior to participation and will be obtained by the principal investigator (PI) or a sub-investigator. After fulfilling the inclusion and exclusion criteria, consent will be obtained.

Randomization and Allocation Concealment

Randomization: Subjects are randomized by simple randomization which remained concealed from the researchers until the end of enrollment. Randomization was done by a random number

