generated computer program using Research Randomizer (Version 4.0) by someone not involved in the research. The randomization schedule was placed in sealed envelopes to be concealed from the researcher until time of consent.

Urbaniak, G. C., & Plous, S. (2013). Research Randomizer (Version 4.0) [Computer program]. <http://www.randomizer.org/>

Blinding

The study is not blinded.

Inclusion criteria

- Patients \geq 18 years of age
- Undergoing clinically indicated elective or non-elective PCI
- Able to swallow oral medications

Exclusion criteria:

- Contraindications to ticagrelor or fentanyl (or other opiates)
- Pregnancy
- Any use of P2Y₁₂ inhibitors within 14 days
- Known coagulation disorders
- Pre-procedural treatment with an anticoagulant (oral anticoagulant or low molecular weight heparin)
- Platelet count $< 100,000/\text{mm}^3$
- Impaired renal function (Estimated glomerular filtration $< 45 \text{ ml/min}/1.73 \text{ m}^2$)
- Impaired hepatic function (Based on medical history)
- Prior or planned transcatheter aortic valve replacement

c. Intervention

Treatment protocol

- All patients will be medicated with at least Fentanyl 25 mcg intravenously prior to start of the procedure. Additional sedation will be at the discretion of the treating physician.
- In the crushed Ticagrelor arm, subjects will receive 180 mg of crushed Ticagrelor, which will be crushed using EZY CRUSH pill crusher and mixed with 30 cc of drinking water, whereas patients in the other arm will receive an integral tablet of Ticagrelor loading dose (180 mg).
- Platelet function testing (PFT) in each patient will be performed (platelet vasodilator-stimulated phosphoprotein assay, multiple electrode aggregometry, Verify Now assay).
- The PFT will be performed at randomization, 30 mins, 2, 4, and 6-hour intervals from the time of Ticagrelor administration. Blood (2cc filled completely) will be collected in blue top tubes (coag sodium citrate 3.29). The platelets must not be disturbed by jarring after collection. The blood must not be shaken after collection, and it must be hand carried to the lab. At each sampling time point, a second blue top tube will be collected for sampling

assurance. The first sample at each time point will be processed. If a testing error occurs, the second sample will be processed for data purposes.

- Patients will be treated according to current American Heart Association / American College of Cardiology guidelines.

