- The choice of the access of the procedure (radial or femoral) and the type of implanted stent will be at the discretion of the operator.
- All patients will receive maintenance doses of ticagrelor (90 mg) twice daily post PCI.

d. Sample Size

This is an exploratory study; therefore, no formal sample size calculation was conducted. The planned sample size is based on feasibility considerations and is considered sufficient to generate preliminary estimates and assess study procedures.

The study plans to enroll 80 participants, 40 participants who had elective PCI and 40 participants who had non-elective (emergent) PCI.

Update to Sample Size 10/31/2025: The study was terminated prematurely on January 27, 2025 due to a poor accrual rate. Challenges were encountered in recruitment in the post-COVID-19 era in the rural community hospital along with increased use of Cangrelor in subjects with ACS. The increased utilization of other therapeutic agents, such as generic prasugrel further reduced the recruitment and relevance of this study.

There were a total of 45 participants randomized at the time the study closed to accrual. Of the 45, seven participants withdrew, leaving a total of 38 participants for analysis. Due to the small sample size, the data from elective (scheduled) and non-elective (emergent) PCI will be combined for analysis to compare crushed versus non-crushed Ticagrelor.

Outcomes

a. Primary Outcomes

The primary outcome is the area under the PFT-time curve (AUC₀₋₆) for the first 6 hours after the loading dose of Ticagrelor.

Platelet Function Testing will be collected at 5 time-points after Ticagrelor administration.

- Baseline (time 0) – immediately prior to ticagrelor loading dose
- 0.5 hours after dose
- 2 hours after dose
- 4 hours after dose
- 6 hours after dose

The actual clock time for each draw will be collected.

The Platelet Function Testing assay will be *VerifyNow Platelet Reactivity Assay* which is used institutionally. Results are reported in platelet reactive units (PRUs). Based on previous studies,

208 will be used as an estimated cutoff to distinguish therapeutic and subtherapeutic platelet inhibition, with PRUs equal to or less than 208 being considered therapeutic⁶.

b. Secondary Outcomes

The secondary outcomes are:

- Stent thrombosis at discharge
- Stent thrombosis at 30 days
- Recurrent myocardial infarction at discharge
- Recurrent myocardial infarction at 30 days
- All-cause mortality at discharge

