- All-cause mortality at 30 days
- Stroke at discharge
- Stroke at 30 days
- TIMI bleeding (minor and major, per TIMI criteria) at discharge
- TIMI bleeding (minor and major, per TIMI criteria) at 30 days

Time-window rules (apply to all endpoints):

“At discharge” = events occurring during the index hospitalization from time of ticagrelor loading dose until the formal hospital discharge time (documented in chart).

“At 30 days” = events occurring from time of ticagrelor loading dose up to 30 days (day 30 inclusive). Events that already occurred during index hospitalization are counted in the “at discharge” endpoint and also contribute to cumulative 30-day counts. The exact event date/time must be recorded.

Events will be identified through review of the electronic medical record, discharge summaries, procedure reports, and 30-day follow-up documentation or contact.

For each outcome, the presence or absence of the event will be recorded for each participant at both time points.

c. Other Prespecified Outcomes

Other prespecified outcomes include:

- Hospital Length of Stay (Hours)
- Hospital Readmission within 30 days

Statistical Analysis

a. General Considerations

Due to the premature termination and small sample size, the data from elective (scheduled) and non-elective (emergent) PCI will be combined for analysis to compare crushed versus non-

crushed Ticagrelor. The analysis of the primary outcome will be per protocol, as it is a sum across five timepoints and any patient with incomplete data would necessarily have a lower score. The remaining tests will be performed on the intention-to-treat sample.

We will report absolute counts and their respective percentages for categorical variables, means and standard deviations for non-skewed numeric variables, or medians and interquartile ranges for numeric variables exhibiting notable skew (assessed graphically). Differences between treatments will be assessed using the Fisher exact test for categorical variables, t-tests for numeric variables exhibiting normality, and Mann-Whitney tests for skewed numeric variables.

The statistical significance of the results will be determined using at a two-sided p-value of less than 0.05. Missing data will be handled with listwise deletion on a test-by-test basis.

b. Baseline Data

Descriptive statistics of the study population will include:

- Demographics (age, gender, race)

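### The primary AUC(0–6) comparison falls to an unadjusted two-sample test on pooled PCI types; the test is valid but leaves PCI type and pre-dose PRU unused

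*SAP*

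**What the plan says.** SAP, Statistical Analysis, c. Primary Outcomes defines AUC(0–6) by the linear trapezoidal rule at actual elapsed times and ends there. The next section, d. Secondary Outcomes, does name a Mann-Whitney test for length of stay. The primary comparison is therefore governed by a. General Considerations: "t-tests for numeric variables exhibiting normality, and Mann-Whitney tests for skewed numeric variables", with skew judged graphically and a two-sided 0.05 level. The protocol's Statistics section offers the same choice, a "t-test when appropriate or the Mann-Whitney U test". Neither document mentions a covariate, a stratified test or an adjusted sensitivity analysis.

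On PCI type, the protocol (Methods & design) plans "Forty patients each in the elective and non-elective PCI groups. Further In each group, patients will be randomized in a 1:1 ratio". The SAP (Randomization and Allocation Concealment) states "Subjects are randomized by simple randomization". After early closure, SAP d. Sample Size says that "the data from elective (scheduled) and non-elective (emergent) PCI will be combined for analysis to compare crushed versus non-crushed Ticagrelor".

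On the pre-dose value, the protocol's Data Collection section lists "platelet function testing at baseline, 30 min, 2, 4, and 6, hours", and SAP Outcomes, a. Primary Outcomes places time 0 just before the loading dose. The SAP's Treatment protocol words the same sample differently: "The PFT will be performed at randomization, 30 mins, 2, 4, and 6-hour intervals from the time of Ticagrelor administration".

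The SAP's baseline list includes MI on admission, a partial marker of non-elective presentation. It names neither PCI type nor pre-dose PRU, though its wording does not exclude them.

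**The concern.** Small numbers are a good reason to pool the two PCI groups. They are not a reason to drop PCI type from the model, where it costs one degree of freedom. The pre-dose PRU is the same assay in the same patient before treatment, yet it enters the analysis only as a small part of the AUC itself.

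What is at stake is precision. At most 38 patients enter the primary comparison, and the SAP says the sample is meant to give preliminary estimates. If either variable predicts AUC(0–6), the unadjusted interval is wider than it need be. Under simple randomisation a chance imbalance in PCI type would also go uncorrected.

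**Working it through.** **Inputs from the documents.** 45 randomised, 7 withdrawn: 45 − 7 = 38, which reproduces the SAP's figure. Two-sided 0.05. Sampling at 0, 0.5, 2, 4 and 6 h. No power, effect size or SD is stated, so there is no such figure to reproduce.

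**Weight of the pre-dose value in the AUC.** The trapezoidal weights are 0.25, 1.0, 1.75, 2.0 and 1.0 h, summing to 6 h. The pre-dose PRU carries 0.25/6 = 4.2%.

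**Assumptions.** 19 elective and 19 non-elective; SD 1 within arm and PCI type; normal errors; correlation ρ between pre-dose PRU and AUC; PCI-type difference g in SD. The effect is set at 0.93 SD because that is what an unadjusted t-test on 19 per arm detects with 80% power (noncentral t gives 0.934).

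**Formulas (equal arms).**
- The unadjusted test sees variance 1 + g²/4, on 36 df.
- The linear model on arm, PCI type and pre-dose PRU sees residual variance 1 − ρ², inflated by 1 + 2/(38 − 2 − 3) = 1.061 for chance covariate imbalance, on 34 df.

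For example, at ρ = 0.5 and g = 0.5:
- unadjusted effect 0.93/√1.0625 = 0.902, power about 77%;
- adjusted effect 0.93/√(0.75 × 1.061) = 1.043, power about 88%.

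Simulation under simple randomisation (at least 20,000 trials per row) runs about a point lower because arm sizes vary:

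| ρ / g | t-test | linear model | change (points) |
|---|---|---|---|
| 0 / 0 | 79.0% | 76.5% | −2.5 |
| 0.2 / 0.2 | 78.2% | 78.0% | −0.2 |
| 0.3 / 0.5 | 76.0% | 79.7% | +3.7 |
| 0.5 / 0.5 | 76.0% | 86.8% | +10.8 |
| 0.5 / 1.0 | 69.1% | 86.7% | +17.6 |

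Adjustment breaks even when the two covariates together explain about 6% of the variance.

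**Interval width.** The 95% CI half-width goes from 0.66 to 0.68 SD at 0/0, and from 0.68 to 0.59 SD at 0.5/0.5.

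**Chance imbalance.** Under simple randomisation with 19 elective among 38, the chance that the elective share differs between arms by at least 20 points is about 26%. It is 19% with 27 elective and 6% with 34.

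**Type I error.** Under simple randomisation the t-test is nominal, at about 5%. If allocation were forced to balance within PCI type, the difference in means would have variance based on 1 while the test estimates 1 + g²/4. The critical value 2.028 then acts as 2.028 × √(1 + g²/4):
- g = 0.5: 2.028 × 1.031 = 2.09, true level 4.4%;
- g = 1.0: 2.028 × 1.118 = 2.27, true level about 3%.

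The linear model stays at about 5% in either case.

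**Skewed AUC.** With lognormal errors (log-SD 0.5), power is as follows:

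| ρ / g | Mann-Whitney | raw-scale linear | rank ANCOVA |
|---|---|---|---|
| 0 / 0 | 89% | 77% | 88% |
| 0.2 / 0.2 | 88% | 79% | 88% |
| 0.5 / 0.5 | 80% | 86% | 91% |

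At log-SD 0.8 with ρ and g both 0 the figures are 97%, 80% and 96%.

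**The case against.** The strongest reply is that nothing here is wrong. The planned test is valid and goes back to the 2019 protocol. The SAP also says "This is an exploratory study; therefore, no formal sample size calculation was conducted", so the trial has no power target to miss. The gain rests wholly on assumed inputs: with weak covariates it is nil or slightly negative, and the large figures need a correlation of 0.5, which a 4.2% weight in the AUC does not guarantee. Most of this stands and limits the point to one of efficiency. It does not remove it, because an exploratory trial aimed at estimates still benefits from a narrower interval, and the loss if the covariates turn out useless is small.

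A reader might go further and infer that the planned test is miscalibrated because the protocol randomised within PCI type. The documents do not support that. The protocol gives a 1:1 ratio in each group and mentions no blocks or forced balance. A separate unblocked list for each PCI group would satisfy both the protocol and the SAP, and the test would then be nominal. The two descriptions are ambiguous rather than plainly contradictory. Even with forced balance, the result would be too few false positives, not too many.

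Timing is the other fair objection. The study is not blinded and was stopped on January 27, 2025. SAP versions 1.0 to 2.1 run from October 15 to December 10, 2025. The documents do not say whether outcomes by arm had been examined, so an adjusted analysis may be able to serve only as support.

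**Conclusion.** The point holds as one of efficiency and specification. The primary test is reached only through a general rule, and two recorded pre-treatment variables are left out of it. Under the stated assumptions (38 patients, half elective, 0.93 SD effect, simple randomisation, normal errors), adjustment is worth between about −2.5 and +17.5 power points. The documents do not show where in that range the trial lies.

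A conservative type I error, about 4.4% at a 0.5 SD PCI-type difference and 3% at 1 SD, would follow only if allocation was balanced within PCI type, which neither document states. It would be wrong to conclude that the planned analysis is invalid, or that adjustment is certain to help. The change is worth making, with medium confidence in its benefit.

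**What to change.** Keep the pooling. In SAP c. Primary Outcomes, name one primary analysis: a linear model of AUC(0–6) on arm, PCI type and the last PRU before the loading dose, reporting the adjusted mean difference with 95% CI and two-sided p-value. Defining the covariate this way also settles the two descriptions of the time-0 sample. Name two sensitivity analyses: the same model on ranks (rank ANCOVA) for skew, and the unadjusted t-test or Mann-Whitney. Tabulate PCI type and pre-dose PRU by arm. State how allocation was done with respect to PCI type.

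Date the amendment and state whether outcomes by arm had been seen. If they had, keep the protocol's unadjusted test as primary and label the adjusted model post hoc and supportive.

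Cost: an amendment and a data-access statement, with no new data. No patient should be lost, because a complete five-point profile already contains the pre-dose PRU. If neither covariate is prognostic, the price is about 2.5 power points. If AUC is markedly skewed and the covariates are weak, the raw-scale model loses about 9–12 points to Mann-Whitney at log-SD 0.5 and 15–17 at log-SD 0.8. The rank version holds that loss to about 1 point, which is why it should be named in advance.
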